9.3. Demographic Characteristics

Descriptive statistics (e.g., N, Mean, Std. Dev., Min, Max) for continuous data types and frequencies for categorical data types will be displayed for the demographic characteristics by randomized treatment assignment and overall. The demographic characteristics and data types are listed below:

Table 9.1: Demographic Characteristics

Characteristic	Data Type
Age at Enrollment (years)	Continuous
Age Group at Enrollment	Categorical
Sex	Categorical
Ethnicity	Categorical
Race	Categorical

The following age group categories will be used: <60, and ≥ 60 years. Subjects may choose more than one Race category.

9.4. Baseline Characteristics

The following baseline characteristics will be summarized using descriptive statistics by randomized treatment group and overall.

9.4.1. Otoscopy Examination

Otoscopy results at screening will be summarized with frequencies and percentages separately for the right and left ear canals according to the following clinical categories:

- Normal
- Blocked, Collapsed
- Abnormal-Not Clinically Significant

- Abnormal-Clinically Significant
- Other

9.4.2. Bone Conduction Audiometry and Tympanometry Results

The bone conduction audiometry results (dB HL) at clinic visit 1 will be summarized descriptively (N, Mean, Std. Dev., Median, Min-Max) separately for each ear at each of the following four frequencies: 0.5kHz, 1 kHz, 2 kHz, and 4kHz.

Tympanometry results at clinic visit 1 will be summarized descriptively (frequencies and percentages) separately for each ear by the following response categories:

- Type A
- Type B
- Type C
- Other

9.4.3. Pure Tone (Air Conduction) Audiometry Results

The pure tone (air conduction) audiometry results (dB HL) at clinic visit 1 will be summarized descriptively (N, Mean, Std. Dev., Median, Min-Max) separately for each ear at each of the following eight frequencies: 250Hz, 500Hz, 1000Hz, 2000Hz, 3000 Hz, 4000Hz, 6000Hz, and 8000Hz. Additionally, the four tone average PTA (averaged across the 500, 1000, 2000, and 4000Hz frequencies separately for each ear) will be computed for each subject and rounded to the nearest whole integer. The ear with the least (i.e., lowest) hearing loss will be used for categorizing subjects into the following categories:

- 15 – 25 dB HL (No Impairment)
- 26 – 40 dB HL (Mild Impairment)
- 41 – 60 dB HL (Moderate Impairment)

9.4.4. Medical History

Relevant medical history information (i.e., Ear/Nose/Throat; Dementia or other neurological condition preventing following instructions; Vascular) will be coded using MedDRA v24.1 and summarized by preferred term.

9.5. Primary Endpoint Analysis

The pivotal primary endpoint analysis will be performed on subjects from the Full Analysis Set (FAS) with supportive analyses also conducted on the Per Protocol (PP) and Complete Cases (CC) Analysis Sets as described below.

Missing data for the IOI-HA score at clinic visit 3 will be assumed to be missing at random (MAR). Under this assumption, the probability that the IOI-HA is missing depends only on available information (e.g., baseline demographic and other baseline characteristics). As such, the first step in modeling the missing data is to perform a logistic regression where the

outcome variable is 0 for observed cases and 1 for missing cases. This logistic regression model will include the following information available at baseline: treatment group, age, sex, race (white vs. not white), pure tone audiometry results (average across the 500, 1000, 2000, and 4000 Hz frequencies for “best” ear (i.e., lowest value of the two ears)), and otoscopy and tympanometry exam results. Factors in this model will be considered significantly related to the probability of missing if the p-value is less than 0.15. PROC LOGISTIC in SAS will be used for this analysis. The otoscopy results will be dichotomized as “normal” vs. “not normal” for the best ear. Likewise, the tympanometry exam results will be dichotomized as “type A” vs. “not type A” for the best ear. Factors which confound with one another may be removed from the model to ensure model stability and convergence.

Once the set of significant factors has been identified via logistic regression, a full information maximum likelihood (FIML) analysis will be performed using PROC CALIS in SAS to estimate the treatment effect after adjustment for significant baseline information. This approach has been shown to produce unbiased parameter estimates and standard errors under MAR [17]. This approach also provides a unique estimate of the treatment difference (PF – SF) and requires fewer decisions than multiple imputation. If there are no baseline factors identified through the logistic regression analysis which are significantly related to missingness and if there is no missing data for any of the baseline factors, the parameter estimate of the treatment effect will be the arithmetic mean difference (PF – SF) between the two groups but with a smaller standard error than using only complete cases.

The process works by estimating a likelihood function for each study subject based on the baseline factors that are present so that all the available data are used. Model fit information is derived from a summation across fit functions for individual subjects, and, thus, model fit information is based on all subjects. With missing data, the FIML fit function [18] is computed for each set of subjects with the same unique pattern of missing values—a casewise likelihood. So, an i subscript is used in the equation below to show that the fit function is for each particular subject:

$$\log L_i = -\frac{k_i}{2} \log(2\pi) - \frac{1}{2} \log|\Sigma_i| - \frac{1}{2} (\mathbf{Y}_i - \boldsymbol{\mu}_i)^T \boldsymbol{\Sigma}_i^{-1} (\mathbf{Y}_i - \boldsymbol{\mu}_i)$$

where \log is the natural logarithm (with base e), π is the mathematical constant, Σ_i is the population covariance matrix, \mathbf{Y} is vector of observed variables, $\boldsymbol{\mu}_i$ is the vector of their means, and the superscript T is the matrix transpose function. The subscripts i denote individual subjects in which the \mathbf{Y}_i vectors differ in length depending on the number of non-missing data values. Similarly, matrices Σ_i and $\boldsymbol{\mu}_i$ vary by deleting rows and columns for missing variables. The sum of the individual log likelihoods is then computed. This process approach allows one to use all the available information in the variables. Additionally, as can be seen from this likelihood function, this approach assumes the IOI-HA scores follow a normal distribution.

Because the study hypothesis is a test of non-inferiority, a Wald-type 95% two-sided confidence interval for the treatment effect will be computed (i.e., treatment effect parameter

estimate +/- 1.96*(Standard error of the estimated treatment effect)) and compared to the non-inferiority margin of 3. If the upper 95% confidence bound for the treatment effect (defined such that higher values favor the pro-fit group) is less than or equal to 3, the null hypothesis will be rejected and the self-fit treatment arm will be considered non-inferior to that of the pro-fit treatment arm.

The pivotal primary endpoint analysis using the above methodology will be based on the Full Analysis Set where all randomized subjects are included in the analysis and subjects will be analyzed according to the treatment group to which they were randomized. A supportive analysis will also be performed using the Per Protocol Analysis Set where subjects will be analyzed according to the treatment received.

A Complete Cases analysis using only those subjects who have a non-missing outcome for the IOI-HA survey will also be performed using a two-sample independent non-inferiority t-test assuming equal variances. The two-sided 95% confidence interval will be reported for the (Pro-Fit – Self-Fit) mean difference. In the event there are substantial departures from the equal variances assumption, a two-sample t-test assuming unequal variances will be performed similarly.

If the non-inferiority hypothesis is rejected using the Full Analysis Set, a gatekeep strategy will be used to test for superiority to determine if the treatment effect (i.e., mean difference) is statistically different than 0 using the same two-sided significance level of 0.05. If the upper two-sided 95% confidence bound for the treatment effect (Pro-Fit – Self-Fit) is less than or equal to 0, superiority of the Self-Fit arm will also be concluded in addition to non-inferiority.

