8.1.2. Study App Data

Study app data is focused on participant fitting including estimated wear time and settings changes during the home intervals.

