6.1. Primary Study Endpoints

The primary endpoint for the study is:

- IOI-HA Clinic Visit 3 scores. The average total IOI-HA scores will be compared between the Self-Fit Group and Pro-Fit Group

The International Outcome Inventory for Hearing Aids (IOI-HA) is a seven-item validated questionnaire designed to be generally applicable in evaluating the effectiveness of hearing aid treatments. The inventory was developed to facilitate cooperation among researchers and program evaluators in diverse settings. The survey has seven items assessing (1) daily hearing-aid use, (2) benefit, (3) residual activity limitation, (4) satisfaction, (5) residual participant restriction, (6) impact (of hearing impairment) on others, and (7) quality of life. Each of the 7 items are scored on a 1 (poorest) – 5 (best) Likert scale and summed to obtain a total outcome score ranging from 5 to 35 where higher scores are better.

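### The missing-data model for the primary endpoint uses baseline factors only and leaves out logged wear time, so unequal loss of low users between arms would bias PF − SF in either direction

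*SAP*

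**What the plan says.** SAP 9.5 states: "Missing data for the IOI-HA score at clinic visit 3 will be assumed to be missing at random (MAR"). It explains this as meaning that "the probability that the IOI-HA is missing depends only on available information (e.g., baseline demographic and other baseline characteristics"). The first step is a logistic regression for missingness: "This logistic regression model will include the following information available at baseline: treatment group, age, sex, race (white vs. not white"), followed by best-ear four-tone average, otoscopy and tympanometry. The retention rule is: "Factors in this model will be considered significantly related to the probability of missing if the p-value is less than 0.15". FIML in PROC CALIS is then used "to estimate the treatment effect after adjustment for significant baseline information". If no factor is retained and no baseline value is missing, "the parameter estimate of the treatment effect will be the arithmetic mean difference" between the arms, which is the contrast among participants with an observed score.

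Protocol 8.1.2 says that the app records "estimated wear time and settings changes during the home intervals". The SAP uses wear in two places: a descriptive table (section 9.2) and the entry rule for the Per Protocol set (section 8). It does not use wear for missing scores. SAP 6.1 lists the first of the seven IOI-HA items as "1) daily hearing-aid use".

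**The concern.** Missing at random is only as credible as the information conditioned on. Under section 9.5, a participant who stops wearing the headphones and then leaves is treated as typical of their arm, given age, sex, race and ear findings. If no factor passes the screen, they are treated simply as typical of their arm.

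The documents suggest that wear is connected to both sides of the problem. For the outcome, one IOI-HA item asks about use, and SAP section 8 defends its minimum wear times as needed for an accurate IOI-HA assessment. For missingness, Protocol 7.1 withdraws participants who cannot wear the headphones comfortably.

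Neither supportive analysis would expose the problem. Complete Cases uses observed scores only, and Per Protocol removes low users. No other missing-data analysis is planned. The same FAS confidence interval also decides the gatekept superiority test, so any bias carries over to it.

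**Working it through.** **The plan's own figures.** The SD and power behind N = 112 are not visible, so N cannot be rebuilt. The loss allowance can be checked: 112 − 90 = 22, and 22/112 = 19.6%. With 45 usable per arm, margin 3, true difference 0 and one-sided 0.025, the implied SD is 3 / [(1.96 + 0.842) × √(2/45)] = 5.08 at 80% power. At 90% power it is 4.39. An SD of 5 is therefore a reasonable working assumption.

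**Algebra.** Let m be the missing share in an arm and D the mean IOI-HA of completers minus that of dropouts. The completer mean exceeds the full-arm mean by m × D. So

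shift in PF − SF = m_PF × D_PF − m_SF × D_SF.

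With the same D in both arms, the 22 planned losses give:

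- 17 SF / 5 PF, D = 3 to 6: −(12/56) × D = −0.64 to −1.29 (toward non-inferiority).
- 11 / 11: 0.
- 5 SF / 17 PF: +0.64 to +1.29 (away from non-inferiority).

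Item 1 spans 4 points, so on its own it contributes at most 4 × 12/56 = 0.86 at the 17/5 split. The sign depends on which arm loses more. Equal m is not enough for zero shift; D must be equal too.

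**Simulation.** Inputs from the documents are 56 per arm, margin 3 and the Wald 1.96 interval. Assumptions are SD 5, wear/IOI-HA correlation (rho) 0.3 to 0.5, and dropout logit = a − slope × wear with slope 1 to 1.5. The planned estimate uses no wear. The auxiliary estimate replaces each arm's completer mean by

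completer mean + b × (mean wear of all randomised − mean wear of completers),

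where b is the pooled within-arm slope of IOI-HA on wear.

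| Loss pattern | Bias of planned PF − SF | Bias with a perfect wear auxiliary |
|---|---|---|
| About 11–14% PF, 27–29% SF | −0.16 to −0.40 | within 0.03 |
| About 11% SF, 27% PF | +0.22 to +0.40 | within 0.03 |
| 20% in each arm, same mechanism | about 0 | about 0 |
| 20% in each arm, wear-driven in SF only (rho 0.5) | −0.55 | not tabulated |

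The auxiliary leaves the empirical SD of the estimate within about 1.5% of its planned value.

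**Error at the margin when Self-Fit loses more.** By approximation, P(Z > 1.96 − |bias|/SD of the estimate). A bias of 0.16 gives about 0.035. For 0.38 with SD 1.026: 0.38/1.026 = 0.37, 1.96 − 0.37 = 1.59, tail 0.056. Direct simulation gives 4.1% to 6.6%, against 2.9% with equal loss; the ML standard error with 1.96 is already slightly liberal. In the reversed pattern the rate falls to 1.1%.

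**Dependence on the assumed mechanism.** A steeper (probit, slope 1.5) dropout curve at 27% SF / 12.5% PF gives −0.26 and −0.46 at rho 0.3 and 0.5, with error rates of 4.8% and 7.1%. At 30% / 9% it gives −0.42 and −0.68, with 6.5% and 10.4%.

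**Imperfect log.** Suppose the log correlates 0.7 with the wear that drives dropout and 30% of dropouts have no log. Then a planned bias of −0.21 to −0.39 becomes −0.16 to −0.27, a reduction of 24% to 31%. A separate run of the rho 0.5 case went from −0.39 to −0.26 (33%).

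**Covariate instead of auxiliary.** With wear assumed 0.5 SD lower in Self-Fit, rho 0.5 and 30% / 9% missing, putting wear on the right-hand side gave bias −1.26 and a 28% false non-inferiority rate. The auxiliary gave −0.01 and 3.3%.

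**The case against.** A reader might infer that the pivotal estimate is biased toward non-inferiority. The documents do not support that. Both arms wear the same headphones, both may adjust settings at home (Protocol 5.2.3), and the comfort-withdrawal rule applies to both. Nothing predicts heavier Self-Fit loss, and heavier Pro-Fit loss makes the test conservative. This objection stands, and the point is conditional because of it.

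The link from low use to dropout is also assumed. Low wear is not a listed discontinuation reason in Protocol 4.8, and a low user who attends Clinic Visit 3 contributes a low score. The design limits the problem: people who prefer not to wear the headphones consistently are excluded, staff contact non-users, and participation lasts 18 to 31 days. This tempers the likely size but does not remove the gap.

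The 112-to-90 allowance concerns usable datasets, so it is not a forecast of missing IOI-HA. Some of the simulated splits slightly exceed it: 13% / 28% of 56 is about 23 losses against 22. The SD, correlation, slope and split are all assumptions.

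Finally, near-zero residual bias is built in when dropout is simulated from the same wear variable that is then added. Protocol 8.1.2 calls wear estimated, and early leavers have little of it. This stands too, which is why the imperfect-log figures are shown.

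The abbreviation e.g. in the missing-at-random sentence leaves room for other information, but the explicit factor list that follows does not use it.

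**Conclusion.** The concern holds as a conditional one. Section 9.5 conditions on baseline factors only, while a collected variable plausibly tied to both score and withdrawal goes unused. Under the stated assumptions (SD 5, correlation 0.3 to 0.5, about 11–14% against 27–29% missing), the bias is about 0.2 to 0.4 points, or 7% to 13% of the 3-point margin, in whichever direction the excess loss dictates. The error at the margin rises to about 0.035 to 0.06 only when Self-Fit loses more. Steeper dropout mechanisms or wider splits give larger values.

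Two further inferences should be resisted. Equal dropout percentages do not guarantee zero bias; the dependence on wear must also match. And adding wear does not eliminate the bias in general: the gain runs from about a third with an imperfect log to nearly all with a perfect one. This is a cheap improvement, not a demonstrated flaw in the result.

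**What to change.** In SAP 9.5, prespecify mean daily logged wear over a fixed window, Home Interval 1, as an auxiliary variable in the pivotal FIML model. Regress it on arm and let its residual covary freely with the IOI-HA residual. State that it is not a right-hand-side covariate, because it is measured after randomisation and adjusting for it would change the contrast. Say how wear is defined for someone who leaves during that interval. Report the baseline-only FIML estimate beside it.

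The cost is one variable in the PROC CALIS model and a few sentences in the SAP; the data are already collected. The downside is slightly more complex code. The change does nothing for participants who leave before any wear is logged, or for missingness that depends on unobserved benefit.

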6.3. Study Hypotheses

The primary endpoint hypothesis for the clinical validation study is as follows:

$$H_0: \text{Mean}(\text{IOI-HA}_{\text{Pro-Fit}}) - \text{Mean}(\text{IOI-HA}_{\text{Self-Fit}}) > 3$$

$$H_1: \text{Mean}(\text{IOI-HA}_{\text{Pro-Fit}}) - \text{Mean}(\text{IOI-HA}_{\text{Self-Fit}}) \leq 3$$

where $\text{Mean}(\text{IOI-HA}_{\text{Pro-Fit}})$ and $\text{Mean}(\text{IOI-HA}_{\text{Self-Fit}})$ are the average follow-up (i.e., clinical visit 3) IOI-HA scores for the Pro-Fit and Self-Fit groups, respectively.

[figure not shown]
The non-inferiority margin of 3 points was determined based on the estimated variation from mean scores previously reported (i.e., mean IOI-HA of 25.5 - 28.9) and is justified because 3 points is within a reasonable margin of variation for the study instrument at the subject level.

7. Statistical Considerations

[figure not shown]

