7.1. Sample Size

Preceding the start of the clinical validation study, approximately participants will be enrolled into a sub-study cohort. These participants will follow the same study procedures outlined in this protocol. After the completion of the sub-study, the clinical validation study

will commence. [REDACTED]

The approach to sample size determination of the clinical validation study is based on a two-sample independent t-test comparing group means assuming equal variances between groups. [REDACTED]

[REDACTED] a total of N=112 (56 per group) will be enrolled in the pivotal portion of the study. To summarize:

Clinical Validation Study: Approximately 112 participants will be enrolled

Sub-Study: Approximately [REDACTED] participants will be enrolled

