7.3. Significance Level

The primary hypothesis test will use a one-sided significance level of 0.025. Analyses of the exploratory objectives will use 95% confidence intervals. Multiple comparison corrections will not be used.

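### SAP 9.5 picks FIML covariates by missingness main effects pooled over the arms, so it is nearly blind to opposite-direction dropout and only partly sensitive to one-arm dropout

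*SAP*

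**What the plan says.** SAP 9.5 assumes that visit 3 IOI-HA scores are missing at random (MAR) and then works in two steps.

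- **Step 1** is a logistic regression of missing versus observed. "This logistic regression model will include the following information available at baseline: treatment group, age, sex, race", followed by best-ear four-frequency hearing level, otoscopy and tympanometry. That is arm plus six baseline factors. No treatment-by-factor term and no arm-specific model is listed. The retention rule is: "Factors in this model will be considered significantly related to the probability of missing if the p-value is less than 0.15".
- **Step 2** is a FIML analysis "to estimate the treatment effect after adjustment for significant baseline information". If no factor passes and baseline data are complete, the estimate is the raw difference in means, Pro-Fit minus Self-Fit.

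The SAP cites FIML as unbiased under MAR. For the decision, "a Wald-type 95% two-sided confidence interval for the treatment effect will be computed", and its upper limit is compared with 3. SAP 7.3 sets the level: "The primary hypothesis test will use a one-sided significance level of 0.025". The Per Protocol analysis repeats the method with its own screen (Table 14.2.1.3). The Complete Cases analysis is an unadjusted t-test. No analysis departs from MAR.

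**The concern.** FIML is unbiased under MAR given the variables in the likelihood. Suppose age drives dropout in one arm only, or in opposite directions in the two arms. That is MAR given arm and age, so it lies within the SAP's own assumption. If the screen drops age, however, dropout is no longer MAR given what is left in the model.

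A main effect pooled over arms is the wrong detector for this pattern. Opposite slopes cancel, and a slope in one arm is diluted. The estimate then falls back towards the raw difference, and the single upper bound that decides the trial moves with it.

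Arm-specific dropout cannot be ruled out here. Participants know their arm (SAP 7.2), and the arms are fitted in different ways. The supportive analyses give no check, because one reuses the screen and the other does not adjust at all.

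**Working it through.** **Inputs from the documents.** Screen terms and p<0.15 (SAP 9.5); margin 3 (SAP 6.3); one-sided 0.025 (SAP 7.3); upper limit of estimate + 1.96 × SE (SAP 9.5); 1:1 allocation (SAP 7.2). For size, "a total of N=112 (56 per group) will be enrolled in the pivotal portion of the study", with at least 90 usable datasets (SAP 4).

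**The plan's own figure.** The usable-data target allows 1 − 90/112 = 19.6% loss; 90/0.8 = 112.5, which rounds up to 113. The SD, power and dropout behind 112 are redacted, so it cannot be reproduced. With 45 scored per arm and a true difference of 0, n = 2·SD²·(1.96 + z)²/3² gives SD 5.08 at 80% power (z = 0.842) and 4.39 at 90% (z = 1.282).

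**Assumptions.** SD 5; 20% missing. One factor x has correlation ρ = 0.3 or 0.5 with IOI-HA and a dropout odds ratio of 2 or 3 per SD (log-odds slope g = 0.693 or 1.099). The documents give none of these.

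**First-order formula.** With missing share p, dropout shifts the mean of x among scored participants by about −g·p. Hence

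unadjusted bias ≈ −ρ·SD·(p_PF·g_PF − p_SF·g_SF).

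- Common slope, equal rates: 0.
- One arm, ρ 0.3, g 0.693: −0.3 × 5 × 0.2 × 0.693 = −0.21.
- Opposite slopes, same values: −0.3 × 5 × 0.2 × 1.386 = −0.42.
- Common slope, ρ 0.5, g 1.099, 30% missing in Pro-Fit and 10% in Self-Fit: −0.5 × 5 × 1.099 × 0.2 = −0.55.

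The formula overstates the bias when slopes are steep.

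**Simulation of the SAP procedure.** There were 6,000 trials per scenario with a true difference of 3, so every rejection is an error. The seven-term screen was followed by regression on scored participants with ML variance and 1.96. This equals FIML when only the outcome is missing. Signs are set so that Self-Fit loses low scorers, Pro-Fit loses high scorers, or both.

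| Dropout pattern | Factor selected | Unadjusted bias | Bias after screen | One-sided error |
|---|---|---|---|---|
| Opposite, ρ 0.3, OR 2 | 16% | −0.39 | −0.32 | 0.057 |
| Opposite, ρ 0.3, OR 3 | 18% | −0.56 | −0.46 | 0.072 |
| Opposite, ρ 0.5, OR 2 | 18% | −0.65 | −0.53 | 0.085 |
| Opposite, ρ 0.5, OR 3 | 19% | −0.94 | −0.76 | 0.126 |
| One arm only (range) | 47–70% | −0.18 to −0.46 | −0.07 to −0.17 | 0.034–0.047 |
| Common slope, equal rates (range) | 90–99% | 0.011 or less in size | 0.010 or less in size | 0.027–0.033 |
| Common slope, 30% vs 10% missing | 99% | −0.43 | 0.00 | 0.027 |
| No relation | 17% | −0.01 | −0.01 | 0.029 |

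**Cross-checks.** Bias after the screen should be about unadjusted bias × (1 − selection rate): 0.387 × (1 − 0.162) = 0.324 against 0.322 simulated, and 0.936 × (1 − 0.186) = 0.762 against 0.757. With SE = 5·√(2/45) = 1.054, a bias of 0.322 gives error Φ(−1.96 + 0.305) = 0.049, and 0.757 gives Φ(−1.96 + 0.718) = 0.107. The simulated 0.057 and 0.126 are somewhat higher, partly because ML variance with 1.96 already gives 0.029 when nothing is wrong. That is a separate, small point.

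**Repairs.** Adjusting for all listed factors left bias of 0.02 or less in size in every common-slope, one-arm and opposite scenario, with error 0.030–0.035.

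The alternative is a two-degree-of-freedom likelihood-ratio test per factor (main effect plus treatment-by-factor term). It was run in 3,000 trials per scenario with slopes 0.7–1.0, correlation 0.3–0.4 and a t-based bound:

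| Pattern | Selected, planned → 2-df | Bias, planned → 2-df | Error, planned → 2-df |
|---|---|---|---|
| Opposite | 17% → 86–98% | −0.34 to −0.58 → −0.01 to −0.05 | 0.052–0.079 → 0.025–0.028 |
| Self-Fit only | 49–65% → 64–83% | −0.09 to −0.15 → −0.03 to −0.06 | 0.031–0.036 → 0.025–0.028 |

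**The case against.** A reader might infer that the screen misses arm-specific dropout in general and mainly finds harmless dropout. Neither half holds.

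- One-arm dropout leaves a pooled main effect, so the factor is selected about half the time or more and a large part of the bias is removed. When both arms have slopes in the same direction but of unequal size, the residual bias is only 0.02–0.03.
- Common dropout is harmless only if the arms lose similar proportions and share the outcome slope. With 30% against 10% missing, the unadjusted difference is biased and the planned screen corrects it.

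The large errors need strong, reversed slopes. Nothing in the documents predicts these: participation lasts 18–31 days (Protocol 1.14), and both arms self-tune at home (Protocol 5.2.3). The 20% loss is about the most that the 90-of-112 target allows; at 10% missing, opposite slopes give error of 0.039–0.044. If the other arm loses the low scorers, the bias runs away from non-inferiority.

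All of this stands, and it limits the point to opposite-direction dropout and, to a lesser degree, one-arm dropout. It does not rescue the procedure, because the SAP's claim of unbiasedness covers every MAR pattern, including these.

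**Conclusion.** The point holds in limited form. The screen is nearly blind to a listed factor that acts in opposite directions by arm (selected in 16–19% of trials). It is partly sensitive to one that acts in a single arm (47–70%).

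Residual bias is about 0.3–0.8 points in the first case and 0.1–0.2 in the second, against a margin of 3. Across both sets of runs, one-sided error is about 0.05–0.13 and 0.03–0.05 when the pattern favours Self-Fit. These sizes rest on the assumed SD, correlation, slopes and missing share. Observed dropout well below 20% would shrink them.

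The documents do not show that such dropout will occur, nor that any error must favour non-inferiority. They do show that the planned step does not guarantee the property claimed for it.

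**What to change.** In SAP 9.5, carry all six listed baseline factors into the FIML model whatever their missingness p-values. Retain the existing allowance to drop confounded factors for stability. Keep the logistic model as a description, and add arm-specific odds ratios to Table 14.2.1.1. The cost is a few degrees of freedom. With the planned 1.96 and ML variance, error when dropout is unrelated to x was 0.033, against 0.029 with the screen.

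If the two-step screen is kept, test each factor separately with treatment in the model. Use a two-degree-of-freedom likelihood-ratio test of the factor plus its treatment-by-factor term at p<0.15. The cost is slightly lower selection of common-slope factors (for example 51% against 58%), with negligible change in bias. The gain comes from the joint test: for one-arm dropout, the interaction term alone detects 48–73%, little better than the present main effect.

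Neither repair helps if the factor's effect on IOI-HA differs by arm. With common dropout and outcome slopes 0.4 SD apart, a bias of −0.37 remained even after adjustment.
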